#### 8.1.3 TREATMENT PERIOD [VISIT 01 THROUGH VISIT 15 (7 +/- 2 DAYS)]

[Purpose]: To monitor safety and wound healing, adjust antibiotic regimens, and administer treatment. At each visit of Visits 01 through 15, if the wound is found to be open, the listed procedures will be performed for the subject.

If the index ulcer is observed to be closed, the subject will continue immediately to Treatment Period Visit 16 and complete all of the procedures listed under Visit 16.

[figure not shown]
If the subject will discontinue from treatment at any of these visits, the subject should move immediately to the end of Treatment Period Visit (Visit 19) and complete all of the procedures listed under Visit 19.

[figure not shown]

[figure not shown]

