#### 8.1.4 TREATMENT PERIOD [VISIT 16 (7 +/- 2 DAYS)]

[Purpose]: To document the index ulcer status of open versus closed.

If a subject's wound is judged to have not closed at this visit the subject will not complete the procedures for this Visit, but will move immediately to complete the End of Treatment Visit (Visit 19) procedures.

If the index ulcer is observed to be closed prior to or at this visit, the following procedures will be completed and the subject will be instructed to return for the Confirmatory Period Visit 17 in (7 +/- 2 days).

[figure not shown]
---

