#### 8.1.5 CONFIRMATORY PERIOD [VISIT 17 AND VISIT 18 (7 +/- 2 DAYS)]

[Purpose]: To confirm complete wound healing for those who demonstrate wound closure during Treatment Period by two consecutive visits, one week apart, providing a total of two observations two weeks apart.

If a subject's ulcer is judged to have re-opened at this visit the subject will not complete the procedures for this Visit, but will complete the End of Treatment Period Visit (Visit 19) procedures.

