### 8.4 ADVERSE EVENTS AND SERIOUS ADVERSE EVENTS

#### 8.4.1 DEFINITION OF ADVERSE EVENTS (AE)

An Adverse Event is any untoward medical occurrence temporally associated with the use of an investigational medicinal product, whether or not considered causally related to that product. An AE can be any unfavorable and unintended sign (for example, an abnormal laboratory finding), symptom, or disease. The Investigator, or his/her designee, will document AEs. AE data will be entered onto the appropriate source and electronic case report form (eCRF). Adverse events will be coded using Medical Dictionary for Regulatory Activities (MedDRA).

All AEs should be followed during the trial period. The Investigator should use his/her discretion in ordering additional tests as necessary to monitor the resolution of such events. Event outcome at resolution or at time of last follow up will be recorded as event resolved, resolved with sequelae, ongoing at discontinuation, or death. Investigators should continue to follow up events of concern outside of the trial per their standard of care. The trial database may be finalized in these cases with events noted as ongoing.

The Investigator should consider adverse events both as they relate to the investigational product and as they relate to the procedures involved in the trial such as debriding tissue. The Investigator is responsible for determining initial relationship, expectedness, and severity of adverse events.

All adverse events must be reported regardless of whether or not they are considered to be related to the test article.

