#### 8.4.4 TIME PERIOD AND FREQUENCY FOR EVENT ASSESSMENT AND FOLLOW-UP

The occurrence of an adverse event (AE) or serious adverse event (SAE) may come to the attention of study personnel during study visits and interviews of a study participant presenting for medical care, or upon review by a study monitor.

All AEs including local and systemic reactions not meeting the criteria for SAEs will be captured on the appropriate case report form (CRF). Information to be collected includes event description, date of onset, clinician's assessment of severity, relationship to study product (assessed only by those with the training and authority to make a diagnosis) confirmed by the Principal Investigator,

and date of resolution/stabilization of the event. All AEs occurring while on study must be documented appropriately regardless of relationship.

Any medical condition that is present at the time that the participant is screened will be considered as baseline medical history and not reported as an AE. However, if the study participant's condition deteriorates at any time during the study, it will be recorded as an AE.

Changes in the severity of an AE will be documented to allow an assessment of the duration of the event at each level of severity to be performed. AEs characterized as intermittent require documentation of onset and duration of each episode.

The Investigator will record all reportable events with start dates occurring any time after informed consent is obtained until the final study visit. At each study visit, the investigator will inquire about the occurrence of AE/SAEs since the last visit. Event outcome at resolution or at time of last follow up will be recorded as "event resolved", "resolved with sequelae", "ongoing at discontinuation", or "death".

---

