Subjects' identified index ulcer will be assessed over the course of the treatment visits (Visit BS and Visits 1 through 16) or until their ulcers close. Subjects whose ulcers have closed, as assessed by the investigator and verified by an independent blinded evaluator using the images collected via the electronic wound imaging and measurement device, prior to the 16th week of treatment (or Visit 15) will stop treatment and return for two consecutive weekly visits (i.e., Visits 17, and 18) to verify if the target ulcer remains closed at these two visits following the initial observation of ulcer closure, which is defined as the complete ulcer closure in this study. Two weeks after the 2nd confirmatory visit (Visit 18), subjects with index ulcer remained as closed at Visits 17 and 18 will return and complete an End of Treatment Period visit (Visit 19). Subjects whose ulcers have not closed at the end of the 16-week treatment (i.e., Visit 16) or whose ulcers have re-opened during the confirmatory visits (Visits 17 and 18) will move on directly to complete the assessments of Visit 19. Visit 19 will serve as the study's End of Treatment (EOT) visit for the treatment and ulcer closure confirmatory period and will also serve as study exit visit.

For those subjects who are enrolled and discontinue from the treatment prior to Visit 16 due to any reasons other than target ulcer closure, Visit 19 will serve as the early termination (ET) visit.

The total duration of study starting from enrollment to the end of the treatment period is 16 weeks, during which time adverse events and ulcer-related complications, including limb amputation are assessed.

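### Safety follow-up ends at a time set by the healing outcome, so the crude complication, amputation and TEAE proportions mix risk with observation time

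*SAP*

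**What the plan says.** SAP 2.2 gives one assessment period for safety. From enrolment to "the end of the treatment period is 16 weeks, during which time adverse events and ulcer-related complications, including limb amputation are assessed".

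The visit rules in both documents tie study exit to the state of the ulcer:

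- **Closure before week 16.** Under Protocol 8.1.3, "the subject will continue immediately to Treatment Period Visit 16 and complete all of the procedures listed under Visit 16". Visits 17 and 18 follow at weekly intervals, and Visit 19 comes two weeks after Visit 18.
- **Re-opening.** SAP 2.2 says that subjects "whose ulcers have re-opened during the confirmatory visits (Visits 17 and 18) will move on directly to complete the assessments of Visit 19". Protocol 8.1.5 agrees: such a subject skips that visit's procedures "but will complete the End of Treatment Period Visit (Visit 19) procedures".
- **No closure.** Under Protocol 8.1.4 a subject still open at Visit 16 "will move immediately to complete the End of Treatment Visit (Visit 19) procedures". Protocol 4.1 confirms that these subjects then leave the trial.
- **Visit 19.** SAP 2.2 makes it the end-of-treatment visit "for the treatment and ulcer closure confirmatory period and will also serve as study exit visit".

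Protocol 8.4.4 records events starting "any time after informed consent is obtained until the final study visit", and SAP 2.6.3 has AEs recorded at every visit. For events still open at exit, Protocol 8.4.1 leaves follow-up to standard care and adds: "The trial database may be finalized in these cases with events noted as ongoing".

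SAP 2.9.4 plans proportions of subjects with ulcer-related complications, amputation and TEAEs. They are split by post-debridement ulcer-size group and, for amputation, also by pathologically confirmed osteomyelitis. Time to first amputation or death is analysed by Kaplan-Meier. The readable text gives no time window for the proportions. It ends the TEAE class at the start of an observational follow-up period, which the design in SAP 2.2 does not contain.

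**The concern.** A proportion of subjects with an event estimates a risk over a stated time only if subjects are watched for about that time. Here the time watched depends on when, and whether, the ulcer closed. A subject who heals early has less time in which to show a complication than one who never heals; a subject who heals after week 12 has more. Two ulcer-size groups with the same weekly risk but different healing speeds would show different crude proportions.

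Two features make this more than a formality. First, recurrent osteomyelitis is a named complication and Protocol 4.1 sets a six-week antibiotic course. If that course starts at baseline, a subject who closes at week 4 and exits at week 8 is seen for 2 weeks after antibiotics, against 10 weeks for a non-closer. Second, a re-opener leaves with an open ulcer, and any later complication or amputation is lost to the trial.

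Safety is part of the primary objective, and the pilot is meant as a framework for a controlled trial. If the same exit rule were carried over, the arm that heals faster would also have the shorter safety follow-up.

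**Working it through.** **1. The plan's own figure.** The Protocol synopsis gives 21 weeks as the longest participation: 1 (screening) + 16 (treatment) + 2 (Visits 17 and 18) + 2 (to Visit 19) = 21. This reproduces, and means 20 weeks from baseline.

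**2. Exit week.** Let k be the week of closure. A confirmed closer exits at k + 1 + 1 + 2 = k + 4, a re-opener at k + 1 or k + 2, and a non-closer at 16.

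| Closure week k | Confirmed closer exits | Re-opener exits | Part of 16 weeks unobserved (confirmed closer) |
|---|---|---|---|
| 4 | 8 | 5 or 6 | 8/16 = 50% |
| 8 | 12 | 9 or 10 | 4/16 = 25% |
| 12 | 16 | 13 or 14 | 0 |
| 16 | 20 | 17 or 18 | 0 (4 weeks beyond) |

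Only closure at week 12 gives a confirmed closer exactly 16 weeks. Week 4 is the earliest closure reported in the retrospective osteomyelitis series (Protocol 2.2, range 4 to 44 weeks). The rules alone would allow closure at week 1 and exit at week 5.

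**3. Unobserved time for the whole trial.** Full follow-up is 36 × 16 = 576 subject-weeks. Confirmed closers lose 36 × p × E[max(0, 12 − k)], where p is the proportion healing. Re-opening and dropout are ignored.

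*Matching series* (Protocol 2.3.2, complex DFU with osteomyelitis): time to heal 16.0 ± 9.3 weeks, 26/33 healed. Assume a lognormal time:
- σ² = ln(1 + (9.3/16.0)²) = 0.291, so σ = 0.540; μ = ln 16.0 − 0.291/2 = 2.627.
- d = (ln 12 − μ)/σ = −0.263.
- E[max(0, 12 − k)] = 12Φ(d) − 16Φ(d − σ) = 12 × 0.396 − 16 × 0.211 = 1.38 weeks.
- Loss = 36 × (26/33) × 1.38 = 39 subject-weeks; 39/576 = 7%.

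*Earliest-closure assumption*: p = 0.8 and all closures at k = 5.53, the mean of the third series (lower-extremity wounds in general). Loss = 36 × 0.8 × (12 − 5.53) = 186 subject-weeks; 186/576 = 32%.

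**4. Effect on a crude proportion.** Assume a 20% complication risk by week 16 at a constant weekly hazard λ = −ln(0.8)/16 = 0.01395. With a proportion p closing at week k, the expected crude proportion is p(1 − e^(−λ(k+4))) + (1 − p) × 0.20. For p = 0.5:
- k = 5.53: 16.2%
- k = 12: 20.0%
- k = 16: 22.2%

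Over p from 0.3 to 0.8 the range is 14.0% to 23.5%. The direction depends on whether closures fall before or after week 12.

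If the hazard halves after closure, the k = 5.53 case gives 15.0% observed against a true 17.0% by week 16, a gap of 2.0 points instead of 3.8. At a quarter of the hazard it is 14.4% against 15.4%. If all events precede closure, early exit loses none.

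**5. Kaplan-Meier for amputation or death.** Take one amputation at week 14. As a crude proportion it is 1/36 = 2.8%. Closers by week 10 have exited by week 14; under the matching series that is 36 × (26/33) × 0.274 ≈ 8 subjects, so the Kaplan-Meier estimate is 1/28 = 3.6%. With half the subjects gone it is 1/18 = 5.6%. The estimator handles unequal follow-up, but it treats those who left as having the same later risk as those who stayed.

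**The case against.** Several points on the other side stand.

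- A reader might infer that events in weeks 16 to 20 are not collected or are outside the analysis. The documents do not support that. Protocol 8.4.4 and SAP 2.6.3 record AEs through the final visit, so the 16-week sentence is a loose statement of the window, not a limit on collection.
- A reader might also infer that the Kaplan-Meier analysis is invalid. It is the right tool for unequal follow-up. What remains is that healing or re-opening triggers the censoring, so it may be informative. The documents give no data on how much.
- Very early exit is unlikely to be common. The series closest to this population averaged 16.0 weeks to heal. The 5.53-week mean comes from the least similar series.
- The crude bias in step 4 assumes unchanged risk after closure. If healed subjects are at lower risk, that bias shrinks, while the informative-censoring worry grows. The two should not be added together.
- The trial is single-arm and descriptive, so no between-arm comparison is biased now. The documents also do not show that complications cluster just after re-opening.
- Text under the safety heading of SAP 2.8, the exposure paragraph of SAP 2.9.4 and parts of Protocol 9.4.4 are blacked out or cut off. A window or exposure adjustment may be there.

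What does not fall away: an adjustment in hidden text could not supply events after study exit, and Kaplan-Meier covers neither complications nor TEAEs nor the separate amputation proportion.

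**Conclusion.** The point holds as a matter of definition and reporting. The stated 16-week period does not match the follow-up that the visit rules deliver, and exit depends on the efficacy outcome. On the readable text, the crude safety proportions have no common observation window.

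The size is probably modest: about 7% of subject-weeks unobserved under the matching series, up to about 32% under the earliest-closure assumption. In the 20%-risk illustration the crude proportion moves by a few points, in either direction. These figures rest on assumed healing proportions and times, a lognormal shape, a constant hazard and no re-opening or dropout.

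The stronger conclusion that the safety results would be invalid is not supported. They would be harder to interpret, mainly across ulcer-size and osteomyelitis subgroups that heal at different speeds, and for re-openers.

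**What to change.** Change the SAP only:

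1. Replace the 16-week sentence in SAP 2.2 with the actual window: first TTAX01 application to each subject's Visit 19.
2. In SAP 2.9.4, report complications, amputation and TEAEs as events per subject-week beside the proportions, overall and by closure status (confirmed closed, re-opened, not closed).
3. For the Kaplan-Meier curve, show numbers at risk and state that subjects without an event are censored at exit, with a note that healing or re-opening can trigger this.
4. End the TEAE class at Visit 19 in place of the undefined observational follow-up date.

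If the blacked-out text already does some of this, only the remainder is needed. The cost is a little more analysis and less simple safety figures; no new data are required.

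Optional: one telephone or chart contact at a common date (week 16 or week 20) for subjects who exit earlier, with priority for re-openers, covering infection, osteomyelitis, amputation and death. This alone recovers events after exit, but needs a protocol and consent change.

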2.3 Schedule of Assessments

The complete schedule of assessments for this study is shown in table below. With reference to the Initial Procedure Visit (Visit BS), study visits are allowed to have a window of ± 2 days for the weekly treatment and confirmatory visits (Visits 01 thru 19).

At Screening, eligible subjects will be assessed for ulcer measurements (i.e., size, perimeter, and depth) and duration of the index ulcer. At the initial visit (Visit BS/baseline), eligible subjects will receive the ulcer care of TTAX01 plus SC. At each of the study visits from Visit 01 through Visit 19, the subject's ulcer measurements (i.e., size, perimeter, and depth) will be assessed, evaluated, and images collected via the electronic wound imaging and measurement device. All of the subjects will receive SC treatment at the clinic at Visit BS and Visits 01 thru 18, and will receive the TTAX01 application at Visit BS or at the last surgery for a staged surgical procedure, and will receive the TTAX01 application(s) at subsequent visits of Visits 01 thru 15 per the guidelines of TTAX01 treatment described in details in the study protocol.

The assessment schedule over the entire study is outlined in the table below.

For more information, contact the Office of the Vice President for Research and the Office of the Vice President for Student Affairs.

This figure is a 2D binary image, likely a mask or a specific pattern for a task. It consists of a grid of 16x16 cells. The vast majority of cells are white. However, there are several black cells arranged in a specific pattern. In the top-left corner, there is a cluster of black cells forming a shape that looks like a stylized 'T' or a 'P'. In the bottom-right corner, there is another cluster of black cells forming a similar shape. There are also several isolated black cells scattered across the grid, particularly in the center and middle-right areas. The overall pattern is roughly symmetric about the center of the grid.

•

1000

2.4 Randomization

This is an open-label study with single-treatment arm. All eligible subjects will be enrolled to receive the treatment. No randomization will be performed.

2.5 Sample Size Estimation

[REDACTED]

2.6 Efficacy and Safety Measurements

In this study, primary efficacy will be assessed using the proportion of subjects with complete ulcer closure over the 16-week treatment period. Secondary efficacy endpoints will include the number of days to complete ulcer closure over the 16-week treatment period, the proportion of subjects with ulcer closure at each of the 16 treatment weeks. The index ulcer will be measured at screening visit and baseline visit (Visit 01) and at each of the post-baseline visits from Visit 02 through Visit 19.

Safety will be assessed through subject early terminations, adverse events, physical examination, clinical laboratory tests (hematology, chemistry), and concomitant medications.

2.6.1 Primary efficacy measure

[REDACTED]

2.6.2 Secondary efficacy measure

The secondary efficacy endpoints are listed below:

Term	Percentage
GMOs	95
Organic	90
Natural	85
Artificial	75
Organic	70
Natural	65
Artificial	60
Organic	55
Natural	50
Artificial	45
Organic	40
Natural	35
Artificial	30

2.6.3 Safety measures

Adverse events are recorded at each visit. A physical examination is performed at screening visit and Visit 19.

The clinical biochemistry and hematology laboratory tests are conducted at screening visit and at Visit 19. Additional laboratory tests are collected at screening visit. Laboratory tests are analyzed by a central laboratory and include the following parameters:

Other safety measures of interest include as follows:

2.6.4 Other measures

Prior treatment for DFU and concomitant medications taken over the course of the study will be recorded throughout the study. Concomitant medications associated with the treatment of the index ulcer will be specifically noted as such.

2.7 Drug Concentration and PK Measurements

No drug concentration measures will be taken in this trial.

2.8 Handling of Missing, Incomplete, and Repeat Data

Primary Efficacy Endpoint: Confirmed complete ulcer closure

Secondary Efficacy Endpoint: Time to complete ulcer closure

[REDACTED]

Secondary Efficacy Endpoint: Complete ulcer closure at each treatment week:

[REDACTED]

Secondary Efficacy Endpoint: Ulcer and granulation tissue measures at each treatment visit

[REDACTED]

Safety Endpoints:

[REDACTED]

[REDACTED]

[REDACTED]

2.9 Statistical Methods

[REDACTED]

[REDACTED]

[REDACTED]

[REDACTED]

[REDACTED]

2.9.1 Primary efficacy analysis

[REDACTED]

[REDACTED]

[REDACTED]

[REDACTED]

| [REDACTED]
| [REDACTED]

[REDACTED]

2.9.2 Secondary efficacy analysis

[figure not shown]
2.9.3 Planned Interim Analysis

No interim analysis is planned.

2.9.4 Safety analysis

Treatment Exposure

Frequencies of exposure to the study treatment will be calculated based on the number of

Early Termination

Adverse Events

Adverse events will be coded for preferred terminologies using Medical Dictionary for Regulatory Activities (MedDRA). AE will be grouped into pre-treatment AE and treatment-emergent AE as well as post-treatment AE and will be reported separately, based upon the start date of the events, the start date of the treatment, and the start date of the observational follow-up period.

Adverse events will be defined as the pre-treatment AEs if they occur prior to the treatment start date; as the treatment-emergent AEs if they occur on or after the treatment start date and prior to the observational follow-up start date; and as the post-treatment AEs if they occur on or after the observational follow-up start date.

Frequency of the treatment-emergent AEs will be calculated for each body system (or system organ class), by preferred terminology, by post-debridement ulcer size group, for number of subjects and percentage reporting the event. The severity of the adverse events and the relationship to the investigational product will be summarized for each body system and preferred terminology by group. Withdrawals due to adverse events will be summarized for each body system and preferred terminology by group and will be listed with demographic variables for individual subjects.

Proportion of subjects who experience ulcer-related complications (e.g., life-threatening, infection-related sepsis complications, recurrent osteomyelitis, development of gangrene) will be analyzed by group.

Proportion of subjects who experience recurrent limb amputation (i.e., full amputation involving the index ulcer anatomic location) will be analyzed by group, respectively, for subjects with and without pathologically confirmed osteomyelitis

Time in number of days to the first amputation on the target limb or foot or death, whichever occurs first, will be analyzed by group, using Kaplan-Meier survival analysis.

Serious adverse events (SAE) (including deaths) will be listed for individual events.

Narratives will be provided for all deaths, non-fatal serious adverse events, and subjects withdrawn due to adverse events.

Physical Examination

[REDACTED]

[REDACTED]

Laboratory Assessments

[REDACTED]

[REDACTED]

[REDACTED]

[REDACTED]

